1.0 Introduction

Acute Pulmonary Embolism

Deep vein thrombosis (DVT) occurs when a blood clot forms in a deep vein, typically in the lower extremities. Pulmonary embolism (PE) occurs when a DVT clot (or fragment) breaks free and travels through the heart to the pulmonary arteries and lodges in an artery causing complete or partial obstruction. Together DVT and PE comprise venous thromboembolism (VTE), a major public health problem in the United States (USA). VTE is the third leading cause of cardiovascular death (1), is estimated to result in 5% to 10% of all hospital death (2), and the third most common cause of preventable hospital death in patients recovering from surgery (3). Using the 2007-9 National Hospital Discharge Survey data, 548,000 hospitalizations were for VTE and of those 278,000 were for acute PE (4). The annual cost of VTE to the US healthcare system is \$7-10 billion for newly diagnosed, medically treated VTE cases (5). PE is associated with a high short-term mortality, requiring a timely and accurate diagnosis for the initiation of antithrombotic therapy. PE is difficult to diagnose on presentation due to the non-specific signs and symptoms for this condition such as cough, shortness of breath, hypoxia, tachycardia, and hemoptysis.

Computed Tomography Angiography

Pulmonary computed tomography angiography (CTA) is the gold standard for the detection of pulmonary emboli (PE) (6), however, radiation exposure and complications related to administering intravenous contrast prohibit universal applicability (7). CTA can detect acute PE with a sensitivity of 90 percent and specificity of 95 percent when combined with CT venography (8, 9). In those who are medically ineligible for CTA, ventilation-perfusion (V/Q) single photon emission computed tomography (SPECT) imaging is commonly acquired to detect PE (10, 11). However, SPECT imaging acquisitions requires transporting the patient to the nuclear medicine clinic, a prolonged acquisition period compared with CTA, and in many hospitals SPECT imaging is not available on weekends or evenings. In this study we will investigate an alternative method to obtain ventilation and perfusion images from respiratory gated non-contrast CT (commonly called 4DCT) that can be performed in the Emergency Department.

^{99m}Tc-MAA SPECT Imaging

Wagner reported the first use of radiolabeled macroaggregates of albumin (MAA) imaged with planar scintigraphy for the detection of pulmonary emboli (PE) causing vascular occlusion (12). MAA is composed of particles ranging in size from 10 to 150 μm that are trapped in the pulmonary microvasculature on their first pass after intravenous injection. Their distribution remains fixed with a biological half-life of 11 h and is dependent on the conditions at the time of injection. ^{99m}Tc-labelled MAA (^{99m}Tc-MAA) imaged with single photon emission computed tomography (SPECT) is considered the standard method for the quantitative determination of pulmonary perfusion (13). Alternative pulmonary perfusion imaging methods include positron emission tomography imaging following administration of ⁶⁸Ge-labeled particles or after bolus injection of ¹³N-N₂ (14). Magnetic resonance imaging (MRI) with contrast agents have been utilized experimentally to image the pulmonary vasculature and tissue perfusion (15). Quantification of SPECT images requires correction of the acquired data for attenuation and scatter (16, 17). One approach is to utilize spatially correlated CT images to determine the attenuation correction, which has lead to the development of SPECT-CT scanners (18). The low-dose CT can be utilized to evaluate the lung airway architecture, lung parenchyma, and pleural space in conjunction with the registered perfusion images rivaling CTA in sensitivity and specificity (19).

Variation in Pulmonary Perfusion with Breathing

[figure not shown]
In a recent study using ^{99m}Tc-MAA SPECT imaging, the difference in distribution due to injection at maximum inspiration versus maximum expiration breath-hold was measured (20). Each subject received SPECT imaging after injection of ^{99m}Tc-MAA in either maximum inspiration or expiration. There was a posterior displacement of the activity centroid in each lung between the expiration

and inspiration images. In another study of normal volunteers MRI perfusion imaging obtained at either maximum inspiration or expiration breath-holds revealed higher perfusion at expiration (15). In a study comparing CT attenuation with SPECT perfusion defects, patients were found to have hypo-attenuated pulmonary regions corresponding to regions with decreased perfusion in 57% of acute pulmonary emboli and 88% of chronic emboli cases (21). In the same study hyper-attenuated regions were found to correspond to regions with hyperperfusion. A method to measure pulmonary perfusion based on subtraction digital fluoroscopy without contrast has been reported (22). In that study subtraction images were generated between chest projection images at systole and diastole generating an image representing the perfusion difference. These perfusion projection images were correlated with 99m Tc-MAA scintigraphy. Thus, changes in the amount and distribution of pulmonary perfusion throughout the respiratory cycle can be expected and these changes may be apparent on dynamic CT.

Imaging Pulmonary Perfusion Defects with 4DCT

Simon (23) described a technique to calculate the change in fractional content of air within pulmonary tissue between anatomically matched CT regions based on a simple model that assumes the density changes were solely due to air content (see appendix A in (24)). We successfully applied that model to inhale & exhale breath-hold CT image pairs (25) as well as 4DCT images (24, 26) to create ventilation images. However, the amount of blood in the thorax and lungs varies with the respiratory cycle increasing with inspiration during normal breathing (27) and decreasing with inspiration with positive pressure ventilation (28). Thus violating the assumption of the model. We found a cyclic variation in the apparent weight of the lung on 4DCT (see figure 1 below (26)) and others have reported respiratory induced variations in pulmonary perfusion of the lung on magnetic resonance imaging (MRI) (29). The pulmonary density changes found on 4DCT thus result from both changes in air and blood content.

4DCT derived ventilation images can also be inferred from the respiratory motion induced local tissue volume changes (24) independent of the 4DCT density values. The Jacobian determinant of the deformation field, calculated from the DIR result of images depicting different respiratory phases of the lungs, is used to estimate the local volume changes or ventilation (24, 30). There is a discrepancy between the density based and the Jacobian based ventilation images suggesting a method to extract respiratory induced blood mass change from 4DCT images. We hypothesize the respiratory induced blood mass change will only occur within perfused lung regions. Each 4DCT image set contains information representing the density change resulting from both ventilation and respiratory induced blood mass changes. Extracting both ventilation and a perfusion-like image from the 4DCT image intensities, referred to as Hounsfield Units (HU), is our goal. However, novel image processing methods are required to extract this information.

of the pulmonary parenchyma (Figure 1) (26). We hypothesize this variation is due to changes in pulmonary perfusion from the respiratory-induced variation in cardiac output (20, 31, 32). We

[figure not shown]

Figure 2. 4DCT RIBMC v. SPECT 99m Tc-MAA Perfusion. A coronal section is shown from a 4DCT derived RIBMC images for a patient with malignant airway stenosis (Left). The corresponding 99m Tc-MAA SPECT coronal section is shown (Right). The cold spot in the RIBMC image coincides with the perfusion defect in the SPECT perfusion image.

defects due to malignant airway obstruction. It is unknown if this process works to detect perfusion defects due to pulmonary emboli, where perfusion is obstructed and ventilation normal.

[figure not shown]

Figure 3. Effect of Positive Pressure Ventilation. Hypothetical expected changes to previously mentioned trends in blood mass observed with spontaneous breathing if the patients are scanned during positive pressure ventilation, such as BPAP.

hypothesize this respiratory induced blood mass change will allow the identification of hypoperfused lung regions. As a preliminary study we created 4DCT RIBMC images from cases with hypoxia induced vasoconstriction, patients with malignant airway obstruction. The resulting images visually compare well with SPECT 99m Tc-MacroAggregates of Albumin (MAA) perfusion images (Figure 2). However, in these cases there are matched ventilation and perfusion

With spontaneous tidal breathing, venous return to the right atrium increases with the decrease in intrathoracic pressure (33) and as a consequence pulmonary arterial blood flow to the lungs increases (34). With positive pressure ventilation the opposite occurs, positive-pressure inspiration decreases the pressure gradient for venous return, which decreases venous blood flow, RV stroke volume, and consequently cardiac output (33). We expect the decrease in lung mass, or pulmonary blood, with normal expiration to become an increase in lung mass with positive pressure ventilation as shown in Figure 3 at the right.

In this study, patients found to have new segmental, lobar or greater perfusion defects, will be imaged with 99m Tc-MAA SPECT/CT and 4DCT to compare perfusion with RIBMC defects.

Hypothesis: Thromboembolic pulmonary perfusion defects on 99m Tc-MAA SPECT/CT will coincide with 4DCT RIBMC defect regions.

Summary & Significance

This is a prospective imaging trial of 20 patients with segmental or lobar pulmonary emboli on CTA. Each will receive 99m Tc-MAA SPECT/CT and 4DCT imaging on the same day. Respiratory induced blood mass change (RIBMC) images will be derived from the 4DCT image and quantitatively compared with the SPECT perfusion images. A 5 patient cohort (cohort 2) to test effect of respiratory pressure on RIBMC was added. A 124 patient cohort (cohort 3) to test the sensitivity & specificity of RIBMC was added. Illustrated in Figure 4 below.

[figure not shown]

Figure 4. Study design. 15 patients (cohort 1) found to have segmental or lobar pulmonary emboli on CTA will be recruited for this study. All enrolled subjects will receive 99m Tc-MAA SPECT/CT and 4DCT imaging. The 4DCT acquisitions will be performed at a single setting to evaluate reproducibility, prior to the SPECT/CT imaging. The primary end-point will be the identification and spatial correspondence of pulmonary perfusion defects on the 99m Tc-MAA SPECT/CT and 4DCT derived RIBMC images. All imaging will be performed on the same day. An additional 5 patients (cohort 2) with the same criteria will be recruited. Each will receive 99m Tc-MAA SPECT/CT imaging as before. They will also receive two 4DCT acquisitions, one with normal breathing and the other with positive pressure breathing using BPAP. 62 patients (cohort 3) found to have PE on CTA and 62 patients negative for PE will be recruited for this study. All enrolled subjects will receive a single 4DCT image acquisition. The 4DCT acquisitions will be performed within 48 hours of the CTA.

2.0 Objectives

- 2.1** The primary objective of this study is to test if 4DCT derived RIBMC images can detect segmental or lobar pulmonary perfusion defects.
- 2.2** A secondary objective is to evaluate the reproducibility and variability of RIBMC images on repeat imaging.
- 2.3** To evaluate the pulmonary blood volume response to positive pressure ventilation versus spontaneous breathing.
- 2.4** The primary objective of cohort 3 is to assess the sensitivity and specificity of contrast-free 4DCT functional imaging for detection of pulmonary emboli.

3.0 ELIGIBILITY, RECRUITMENT, AND SELECTION

Patients with CTA proven segmental or lobar pulmonary emboli will be recruited for this study. Subjects will not be excluded based on age, gender, gender identity, sexual orientation, economic status, race or ethnicity.

3.1 One cohort of 15 patients and another of 5 patients (20 patients total) with CTA proven segmental or lobar pulmonary emboli will be consented for the study and registered on the protocol. Patients may have started anti-coagulation therapy prior to enrolling.

3.1.1 Inclusion Criteria

3.1.1.1 Patients with segmental or lobar pulmonary emboli on CTA identified within past 48 hours.

3.1.1.2 May have initiated anticoagulation therapy.

3.1.1.3 Patients must sign informed consent to enter this study.

3.1.1.4 Documented not pregnant if child-bearing age woman.

3.1.2 Exclusion Criteria

3.1.2.1 Patients unable to tolerate two 15-minute (4DCT) and one 30- minute imaging sessions (SPECT/CT) in the same day.

3.1.2.2 Unable to sign informed consent due to cognitive impairment or health status.

3.1.2.3 Patients who are unstable from a respiratory status requiring ICU care.

3.1.2.4 Patients who receive tissue plasminogen activator.

3.1.3 Patients who are <18 years old.

3.2 One cohort of 124 patients who present to the Emergency Center with suspected pulmonary emboli. We will recruit patients 62 positive and 62 negative for pulmonary emboli on CTA.

3.2.1 Inclusion Criteria

3.2.1.1 Patients who are scheduled to receive, or who have received, CTA for suspected pulmonary emboli within past 48 hours.

3.2.1.2 May have initiated anticoagulation or tissue plasminogen therapy.

3.2.1.3 Patients must sign informed consent to enter this study.

3.2.1.4 Documented not pregnant if child-bearing age woman.

3.2.2 Exclusion Criteria

3.2.2.1 Patients unable to tolerate one 15-minute (4DCT).

3.2.2.2 Unable to sign informed consent due to cognitive impairment or health status. Patients who are <18 years old.

4.0 STUDY EVALUATIONS

Study patients will receive 4DCT imaging after signing consent, followed by ^{99m}Tc-MAA SPECT/CT, and a second 4DCT imaging session.

4.1 **4DCT ACQUISITIONS***. The patients will be imaged lying supine and flat on the scanner bed with their arms above their head. On a multislice CT scanner, CT images will be obtained through the entire lung during resting tidal breathing while the patient's respiration is monitored with an external device for respiratory gating using the standard over-sampled spiral 4DCT acquisition method ([35](#), [36](#)). The 4DCT acquisition will be acquired in duplicate at standard low dose.

4.2 **4DCT ACQUISITIONS W/ BPAP**. The patients will be fitted with a face mask covering mouth and nose. The expiratory positive airway pressure (ePAP) will be set to 4 cm H₂O and inspiratory positive airway pressure (iPAP) to 12 cm H₂O. A 4DCT will be acquired as described in the previous section. The patients will undergo BPAP for <10 minutes. Upon completion of the scan the patients will resume normal breathing of room air.

4.3 **^{99m}Tc-MAA SPECT/CT ACQUISITIONS***. The patients will undergo ^{99m}Tc-MAA SPECT/CT pulmonary perfusion imaging in the nuclear medicine clinic using the

standard clinical procedure under the supervision of a Beaumont nuclear medicine physician. This will include SPECT/CT imaging using ^{99m}Tc -labeled macro-aggregated albumin (^{99m}Tc -MAA), an FDA approved radiopharmaceutical in routine clinical use at Beaumont. The dose and administration will be prescribed by the nuclear medicine physician. A CT will be acquired for attenuation correction and image registration purposes and is a standard part of this procedure. The patients will be imaged supine with arms above their head. This scan will be performed on the same day as the 4D CT scans.

*If any incidental findings are noted, that have not been previously reported, the researcher will discuss these with the patient's treating clinical physician who will determine appropriate follow up.

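### Cohort 2 breathes on BPAP within days of a pulmonary embolism, with no blood pressure criterion, measurement or stopping limit, and Section 8 does not mention BPAP

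*Combined protocol and SAP*

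**What the plan says.** The Figure 4 caption in Section 1.0 sets up the cohort: "An additional 5 patients (cohort 2) with the same criteria will be recruited". Each patient has two 4DCT scans, "one with normal breathing and the other with positive pressure breathing using BPAP". The criteria are therefore those of Section 3.1, starting with 3.1.1.1: "Patients with segmental or lobar pulmonary emboli on CTA identified within past 48 hours".

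The BPAP scan serves objective 2.3: "To evaluate the pulmonary blood volume response to positive pressure ventilation versus spontaneous breathing". No treatment purpose is given for it.

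Section 4.2 fixes the expiratory pressure at 4 cm H2O and the inspiratory pressure at 12 cm H2O, and limits the time: "The patients will undergo BPAP for <10 minutes". Patients then go back to breathing room air unassisted.

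Section 1.0 gives the physiology on which the experiment relies: "positive-pressure inspiration decreases the pressure gradient for venous return, which decreases venous blood flow, RV stroke volume, and consequently cardiac output".

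The entry criteria nearest to a stability check are 3.1.2.1 ("Patients unable to tolerate two 15-minute (4DCT) and one 30- minute imaging sessions") and 3.1.2.3 ("Patients who are unstable from a respiratory status requiring ICU care"). Section 3.1.2.4 also keeps out patients given tissue plasminogen activator.

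Section 8 describes participation as one SPECT/CT and two 4DCTs. The risks it names are radiation and claustrophobia.

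**The concern.** The circulatory effect of positive pressure is the reason for the BPAP scan. The protocol expects a change in pulmonary blood content because it expects venous return and cardiac output to fall. It produces this effect for research, in patients whose pulmonary arteries were recently found to be obstructed. One would expect the same document to say who should not have the manoeuvre on circulatory grounds, what is measured while it is under way, and when it stops.

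Participant safety and the completeness of the risk section are at stake; the validity of the results is not. A patient who feels unwell can stop. The gap concerns the patient whose pressure is already low, or falls without symptoms, because the written plan does not require anyone to take a reading.

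**Working it through.** There is no stated figure to reproduce. The check sets the provisions side by side and then sizes the exposure.

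**Step 1. Does any provision for cohort 2 concern the circulation?**

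| Provision | What it covers | Haemodynamic? |
|---|---|---|
| 3.1.1.1–3.1.1.4 | Embolism on CTA, anticoagulation allowed, consent, not pregnant | No |
| 3.1.2.1 | Tolerance of the imaging sessions; can be read to include the BPAP scan | No |
| 3.1.2.2 | Inability to consent, including because of health status | No; may exclude some very ill patients |
| 3.1.2.3 | Respiratory instability needing ICU care | No; limited to respiratory status |
| 3.1.2.4 | Tissue plasminogen activator given | No; depends on a treatment, not on blood pressure |
| 3.1.3 | Age under 18 | No |
| 4.1 | Respiration monitored, for gating | No |
| 4.2 | Mask, pressures, duration | No vital signs or early-stop rule |
| 5.1 | Removal for an adverse event, at the treating physician's discretion | No limit stated |
| 5.2, 5.3 | Intolerance of imaging; patient choice | No; rely on the patient |
| 5.4 | Image quality | No |
| 6.2 | Evaluation before registration | Content not specified |
| 10.1, 10.4, 10.5 | Adverse event review and reporting | No; act after an event is recognised |

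None of the nine entry criteria (4 + 4 + 1) or the four removal criteria is haemodynamic. Several concern unrelated matters such as consent, pregnancy and image quality, so the counts show absence and do not measure risk.

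**Step 2. Apply the text to one patient.** Take an adult with a segmental embolism found the day before, systolic pressure below 90 mmHg, able to consent and lie still, needing no ICU care for breathing, and not given tissue plasminogen activator. Every entry criterion is met. Section 6.2 might bring the low pressure to light, but no criterion would then exclude the patient. BPAP starts under 4.2 with no reading required. If pressure falls without symptoms, 5.2 and 5.3 are not triggered, and 5.1 and 10.1 act only if someone has noticed.

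**Step 3. Section 8 against 4.2.** Section 4.2 adds a mask and positive pressure to one of the two 4DCTs. Section 8.2 discusses both 4DCTs and names radiation only. The effect described in Section 1.0 is not carried into the risk section.

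**Step 4. Size of the exposure.**
- Planned participants: 15 + 5 + 124 = 144. Exposed to BPAP: 5/144 = 3.5%.
- Total BPAP time: 5 patients × under 10 minutes = under 50 minutes.
- The documents give no event rate and no size for the fall in cardiac output, so no risk estimate can be made.

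**The case against.** The strongest reply is that the protocol is not without protection. Tolerance, respiratory stability, the plasminogen activator exclusion, the consent-capacity exclusion on grounds of health status and the evaluation before registration probably remove some of the sickest patients. The return to room air after BPAP suggests, without proving, that patients on respiratory support were not intended. There is a treating physician, and adverse events are reviewed and reported. The exposure is short, at stated pressures, in five people. Section 8 also looks as if it was not updated when cohorts were added, since its description does not fit cohort 3 either, and 8.2 names the major risk without claiming to be exhaustive.

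Most of this stands, and it is why the point is minor. It does not supply a circulatory criterion, a required measurement or a BPAP entry in Section 8.

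A reader might infer more, and the documents do not support it:
- **That BPAP at 4/12 cm H2O is dangerous in these patients.** Section 1.0 gives the direction of the effect, not its size, and makes no statement of hazard.
- **That a fall in pressure would go unseen.** The protocol does not describe routine clinical monitoring. It is silent on measurement, which does not show that nobody measures.
- **That patients are not told about BPAP.** Section 6.1 requires the risks to be explained, and the consent pages are not in the review copy.
- **That the results are compromised.** No sample size or endpoint calculation depends on this point.

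**Conclusion.** The concern holds in a limited form. A research-only manoeuvre with a circulatory effect that the protocol itself describes is given to patients with recently found pulmonary embolism. No entry, monitoring or stopping provision is haemodynamic, and the risk section does not mention the manoeuvre. Followed as written, the plan could admit a hypotensive patient to BPAP with no blood pressure reading required, and a fall without symptoms might not be detected.

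The severity is low. The exposure is 5 of 144 participants and under 50 minutes in all. How often a hypotensive patient would be recruited cannot be told from the documents. The view that such a patient has less reserve for a drop in cardiac output is a clinical judgement, not something the documents state.

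**What to change.** Three additions, for cohort 2 only:

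1. **Section 3.1.2.** Exclude hypotension, for example systolic pressure below 90 mmHg, or current vasopressor or inotrope use. The 90 mmHg figure is an assumption (plausible range 90 to 100 mmHg) for the clinical investigators to confirm.
2. **Section 4.2.** Record blood pressure, heart rate and oxygen saturation before BPAP, on BPAP and after mask removal, with automated cuff and oximeter readings continued through the acquisition where feasible. Without readings during the acquisition, a silent fall could be missed until the mask is off. Do not start BPAP, or stop it, at limits set by the clinicians or on new faintness or chest pain. Then notify the treating physician, who can decide on removal under 5.1.
3. **Section 8.** Add a BPAP subsection stating the effect described in Section 1.0 and these safeguards. This needs no threshold and could be adopted alone.

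No change of scan order is proposed. Section 4.0 and the Figure 4 caption do not agree on the order, but that is a separate matter.

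The cost is one amendment and at least 3 × 5 = 15 sets of vital signs. The protocol does not say who runs the BPAP scan, so the sponsor should confirm that someone present can take the readings and act on them. A reading on BPAP before acquisition uses part of the 10-minute limit. A candidate may become ineligible, and a stopped scan may leave fewer than five normal/BPAP pairs for objective 2.3. Cohorts 1 and 3 and all endpoint calculations are unchanged.
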